#### 1. Purpose and Objectives

The proposed study will evaluate the response and remission rates for major depressive disorder (MDD) in chronic kidney disease (CKD) patients treated with bupropion or fluoxetine for 12 weeks. In addition, the study will document the relative tolerability and safety, and longitudinally contrast the effects of bupropion and fluoxetine on measures of cognitive function, fatigue, inflammation, and tryptophan (TRP) and TRP catabolites in blood. It is hypothesized that both drugs will significantly reduce MDD symptoms from baseline, and be tolerable and safe, but bupropion will be associated with greater reduction in proinflammatory cytokines, cognitive impairment, and fatigue compared with fluoxetine.

#### The Specific Aims of this study are:

Aim 1: Determine the efficacy of bupropion and fluoxetine in treatment of MDD in CKD patients.

**Aim 2**: Determine whether longitudinal change in MDD symptoms, cognitive dysfunction, and fatigue differ between bupropion and fluoxetine.

**Aim 3**: Determine whether longitudinal change in MDD symptoms, cognitive dysfunction, and fatigue correlate with change in inflammation, measures of TRP availability to brain, or neurotoxic TRP metabolites.

# Hypotheses:

- 1) Bupropion and fluoxetine will both show efficacy in treating MDD;
- 2) Bupropion will lead to greater improvement in cognitive dysfunction and fatigue than fluoxetine; and
- 3) Change in cognition and fatigue over time will correlate with change in C-reactive protein (CRP) and quinolinic acid and change in overall depression score will correlate with measures of TRP availability.

# 2. Background

Depressive symptoms, major depressive disorder (MDD), fatigue, and cognitive dysfunction are among the most common symptoms in patients with chronic kidney disease (CKD). In one study, 71% of ESRD/HD patients had MDD [1], although lower rates were reported when structured diagnostic interviews were used to diagnose [2]. Even when the full criteria for MDD are not met, most ESRD/HD patients suffer from moderate to severe depressive symptoms. ESRD/HD patients also show high rates of cognitive dysfunction, with up to 87% showing some cognitive impairment and 37% showing severe impairment [3].

There have been few controlled trials for treating MDD in CKD patients [18], although uncontrolled studies are encouraging. The relative safety of selective serotonin reuptake inhibitor (SSRI) drugs such as fluoxetine led to its use in several positive open label studies [19-26]; however the one placebo-controlled trial failed [27]. While SSRIs are efficacious in treating MDD in patients with chronic general medical conditions, symptoms of fatigue and cognitive dysfunction are often unresponsive [28, 29]. Bupropion is a unique antidepressant, being a selective norepinephrine (NE) and dopamine (DA) reuptake inhibitor. These properties may underlie its relative advantage to SSRIs in improving fatigue and cognition. Bupropion is efficacious in MDD [30], attention deficit disorder [31], and improves cognitive dysfunction in MDD patients [30]. Bupropion's selectivity for NE/DA, and the modulation of prefrontal cortex attention/cognition and limbic reward circuits by NE/DA may underlie its favorable profile on cognition, fatigue, energy, weight, and sexual function.

MDD is not a single disease, but a genetically complex syndrome with many causal pathways [4]. While early research focused exclusively on monoamines, pro-inflammatory pathways are now known to play a role, being capable of inducing depressed mood, fatigue, and cognitive impairment [5-7]. This line of research has been complicated in part by the variate sources of inflammation for a given individual, (e.g. age, gender, weight health status, allergies, environment, medications, mental health, substance, etc). For instance the most common cause of inflammation is presence of dental disease. Tryptophan (TRP) depletion, pro-inflammatory cytokines, and neurotoxic TRP metabolites affect the brain circuits involved in depression and cognitive function [8]. Experimental depletion of the essential amino acid TRP can induce depressive symptoms, anorexia, fatigue, and cognitive dysfunction in humans [4, 9] due to reductions in brain serotonin (5-HT) [10] while administration of lipopolysaccharide (LPS) induces depressive

Version #: 17, IRB #203076

PI: [name]

symptoms, fatigue, and cognitive impairment through direct effects of pro-inflammatory cytokines on brain circuits. Many of these effects can be blocked by antidepressants [6].

Elevated levels of pro-inflammatory cytokines, including tumor necrosis factor- $\alpha$  (TNF- $\alpha$ ), interleukin-1 $\beta$  (IL-1 $\beta$ ), and IL-6 are prominent features of HD [11, 12]. Reduction in total plasma TRP is also a well documented abnormality in CKD patients [11], with plasma levels of total TRP as low as those that are associated with depressive reactions induced by experimental TRP depletion in humans [8]. Elevated TNF- $\alpha$  and IL6 have direct effects on the central nervous system and increase peripheral conversion of TRP to the neurotoxic catabolites kynurenine (KYN) and quinolinic acid [13] [14]; in part by inducing an increase in the activity of the enzyme indoleamine 2,3-dioxygenase (IDO). While total TRP is low, free TRP levels can increase in blood between dialysis treatments [15], further driving its metabolic conversion to KYN and quinolinic acid. KYN and quinolinic acid levels are known to be markedly increased in ESRD/HD patients [16], plausibly contributing to the depressive symptoms, fatigue, and cognitive impairment [17].

Independent of its effects on cognition and fatigue through NE/DA mechanisms, bupropion may have anti-inflammatory actions that could further enhance its efficacy in reducing cognitive dysfunction and fatigue secondary to inflammation. This is suggested by its ability to reduce TNF- $\alpha$  in mice challenged with LPS [33] and to reduce inflammation and improve mood in patients with atopic dermatitis [34]. Bupropion also reduced TNF- $\alpha$  in patients with Crohn's disease and chronic hepatitis B virus infection [35, 36]. While there are no trials of bupropion in ESRD/HD patients with MDD, a retrospective review suggested bupropion might be beneficial [37]. This proposal will obtain preliminary data needed to fully justify and design a definitive trial of bupropion in ESRD/HD patients with MDD.

Lastly, it is well known that depression has a mutually enhancing relationship with pain. As chronic pain is associated with depression and other psychiatric syndromes, and in turn depressed patients endorse somatic symptoms, mainly pain. This is particularly relevant to our study population, since approximately half of the patients with chronic kidney disease suffer from chronic pain, and frequently increased inflammation is the main suspected mechanism.

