# **4. Study population** is defined as CKD patients with chronic kidney disease with MDD. **Inclusion Criteria**

- age 30-70 vrs:
- meet the Diagnostic and Statistical Manual of Mental Disorders, 4th Edition (DSM-IV) criteria for MDD;
- have a Ham-D score > 17
- if receiving any of these medications, on a stable or maintenance dose of iron or erythropoietinstimulating agents, statins, angiotension receptor blockers and/or angiotension converting enzyme inhibitors, phosphate binders and vitamin D receptor analogs as these agents may influence cytokines proposed in the study;
- serum albumin of ≥ 3.2 g/dl, serum phosphate of <6.5 mg/dl, and serum hemoglobin of ≥9 mg/dl in two consecutive blood tests [subjects failing screening due to these blood tests will be allowed to be re-screened in 30 days];

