# For patients not on HD or Peritoneal Dialysis

• Estimated glomerular filtration rate below 59 mL/min per 1.73 m^2.

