#### For patients on HD

- have patent and non-infected arteriovenous fistula or graft;
- are receiving maintenance HD 2-3 times per week;

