# Recruitment Process—Identifying Potential Subjects

Subjects will be recruited from the UAMS Kidney Center, other outpatient UAMS clinics, UAMS Hemodialysis Center and other local dialysis centers using flyers, electronic dissemination of the flyer to UAMS physicians and/or newspaper ads. Referring physicians will be invited to provide the information to patients who they feel are appropriate for the study and, if the patient expresses an interest in participation or obtaining more information, the physician will provide the contact information of the study staff to the patient, who will voluntarily choose whether to contact the study staff for screening. Release of information/consent documents will be obtained prior to accessing patient clinical information. Prior to beginning the protocol and after obtaining patient's consent, study physicians will discuss the merits of a patient's participation in the study with the patient's hemodialysis physician.

Patients seeking information about the study will initiate phone contact with study staff for initial screening regarding inclusion and exclusion criteria. A partial HIPAA waiver will be requested from the IRB for phone screening purposes only. Subsequent access to clinical information will require written release of information/consent by the patient.

Each potential subject will contact the study staff by phone for initial screening regarding inclusion and exclusion criteria. Patients, who appear to meet inclusion and exclusion criteria and indicate agreement for the study team to contact their treating physician, will be scheduled to come in for a face-to-face meeting, be provided with study information, sign informed consent/HIPAA Authorization and undergo initial evaluation. After consent/authorization is signed by the subject, the research staff will contact the treating physician to discuss the subject's participation, provide medical records release, and obtain medical information from the treating physician.

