## 6. Research Plan

The current study proposes to recruit up to 50 participants in order to have 40 completers. Eligible CKD patients with MDD will be randomly assigned to 12 weeks of open label, flexible dose treatment with either Bupropion SR (N=20) or Fluoxetine (N=20). Patients will be recruited from the UAMS dialysis center or other local dialysis centers via flyers, referral by their treating physician and/or newspaper ads. Written consent will be obtained before any study procedures. Subjects are randomly assigned to open label treatment with one of the following:

• Bupropion group:

Version #: 17, IRB #203076

PI: [name]

 For patient not on hemodialysis or peritoneal, oral administration of bupropion SR tablet at a dose of 150 mg daily. Bupropion SR doses will be adjusted upward or downward based on tolerability and response.

- For patient on hemodialysis or peritoneal dialysis, oral administration of bupropion SR tablet at a dose of 150 mg on the 1st and the 3rd dialysis day of each week. Bupropion SR doses will be adjusted upward or downward based on tolerability and response.
- Fluoxetine group: Oral administration of fluoxetine tablet will be started at a dose of 10 mg/day for the
  first week and then increased, as tolerated to 20 mg/day for weeks 2–4. After this, doses will be
  adjusted based on clinical response and side effects up to a maximum dose of 60 mg/daily by week
  10.

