General Methods: Given that a primary goal of the current study is to obtain data to justify and support the feasibility of a future definitive trial, a variety of data necessary for this, including data on tolerability and safety (see below), will be obtained. For example, subject disposition will be summarized with a table indicating the number of subjects screened, the number of screen failures by reason, the number enrolled, the number who dropped out (by reason), and the number completing the study. Random double-blind assignment of patients to fluoxetine or bupropion is expected to yield similar distributions of measured and unmeasured variables of interest. This design provides a strong basis for making inferences about causal relationships between variables by controlling a priori for a wide range of patient and situational factors, thereby increasing the validity of estimates and inferential tests. In betweengroups analyses, variables that are related to outcome which differ between groups will be included as predictors in a logit model predicting group assignment, and the predicted values of this model will be incorporated as a covariate in all subsequent analyses. This includes factors that could influence treatment response [125-127], including number of prior episodes (>2 or not), treatment response vs. remission during treatment, and sex [128]. Continuously distributed outcomes will be summarized with the sample size, mean, standard deviation, median, minimum and maximum and categorical or binary outcomes with counts and percentages. Distributions will be examined to identify potentially influential observations (outliers) and suggest transforms (e.g., log) to normalize. The final report containing formatted tables and embedded graphics will be produced in Microsoft Word directly from the database using the SAS Output Delivery System. Analyses will use all subjects with usable data. All statistical testing will be two-sided with a significance level of 5%. The Holm-Bonferroni step down method will be applied as necessary to correct for multiple testing. SAS Version 9.2 for Windows (SAS Institute, Cary, North Carolina) will be used throughout.

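### The pilot is to inform an ESRD/HD trial but enrols dialysis and non-dialysis CKD patients, and no dropout or tolerability summary is planned by dialysis status

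*Combined protocol and SAP*

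**What the plan says.** Section 2 (Background) states the purpose of the pilot: "This proposal will obtain preliminary data needed to fully justify and design a definitive trial of bupropion in ESRD/HD patients with MDD". General Methods, in the data analysis section, repeats the design purpose without naming a population: "a primary goal of the current study is to obtain data to justify and support the feasibility of a future definitive trial". Section 3 (Study Design) makes weeks of treatment completed an outcome and wants a dropout estimate for the later study, again without naming its population.

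The enrolled population is broader. Section 4 "is defined as CKD patients with chronic kidney disease with MDD", with three routes of entry:

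- not on dialysis: "Estimated glomerular filtration rate below 59 mL/min per 1.73 m" squared;
- on HD: "are receiving maintenance HD 2-3 times per week", with a usable fistula or graft;
- on PD: two months of kept outpatient visits.

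No quota or minimum by dialysis status is given, and no stratified randomisation is described.

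The recruitment sources differ between sections. The Recruitment Process lists "UAMS Kidney Center, other outpatient UAMS clinics, UAMS Hemodialysis Center and other local dialysis centers". Section 6 (Research Plan) says "Patients will be recruited from the UAMS dialysis center or other local dialysis centers", by flyers, physician referral or newspaper advertisements.

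On analysis, General Methods plans one disposition table and mentions no split by dialysis status. Tolerability and Safety compares adverse events and withdrawals between medication groups. Exploratory Analyses lists age, sex, baseline Ham-D and baseline dental disease as covariates.

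**The concern.** Dropout and tolerability are the figures that the pilot is expected to hand to the next trial. If that trial is in ESRD/HD, the relevant rates are those of dialysis patients. Followed as written, the plan produces no such rates: it gives figures overall or by drug, for a mixture whose composition is left to recruitment.

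The protocol itself gives reasons to expect the groups to differ. Bupropion starts on a different schedule on and off dialysis. Recorded noncompliance with dialysis schedules is an exclusion and PD patients must have kept their visits, while non-dialysis patients face no comparable adherence screen. Consent and blood draws can take place at the dialysis site, so visit burden may differ too. A dropout rate taken from the wrong mixture would mis-size the enrolment of the later trial.

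**Working it through.** **Inputs from the documents.** Up to 50 enrolled for 40 completers (Sections 3 and 6). Bupropion SR starts at 150 mg daily off dialysis, and at 150 mg on the 1st and 3rd dialysis day of each week on HD or PD (Section 6).

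**Inputs assumed.** The documents give neither the share on dialysis nor any rate by dialysis status, so the values below are illustrations.

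**The plan's own figure.** 10/50 = 20% dropout, and 40/(1 − 0.20) = 50, so the enrolment target is consistent with 20% dropout. The point does not rest on the power calculation, which reproduces closely for Hypothesis 1 (0.765 by paired t-test, against 0.78 stated).

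**Regimens.** Nominal starting amounts are 150 × 7 = 1050 mg/week off dialysis and 150 × 2 = 300 mg/week on dialysis, a ratio of 3.5. This is a ratio of milligrams, not of exposure: the Background reports a more than twofold metabolite AUC in HD patients. It is used here only to show that the bupropion arm contains two regimens, and no view is taken on dosing.

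**Effect of not splitting.** With f the dialysis share, the overall rate is f × d(dialysis) + (1 − f) × d(non-dialysis). Its difference from the dialysis rate is (1 − f) × [d(non-dialysis) − d(dialysis)].

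| Assumed dropout, dialysis / non-dialysis | f = 25% | f = 50% | f = 75% |
|---|---|---|---|
| 30% / 10% | 15% (15 points too low) | 20% (10 too low) | 25% (5 too low) |
| 25% / 15% | 17.5% (7.5 too low) | 20% (5 too low) | 22.5% (2.5 too low) |
| 10% / 30% | 25% (15 too high) | 20% (10 too high) | 15% (5 too high) |

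The error is zero if the two rates are equal or everyone is on dialysis.

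**Consequence for a later trial, f = 50%.** Planning on 20% inflates enrolment by 1/0.80 = 1.25. If the dialysis rate is 30%, the factor needed is 1/0.70 = 1.43, and 1.25 × 0.70 = 0.875, so completers fall 12.5% short. If the dialysis rate is 10%, 1.25 × 0.90 = 1.125, a 12.5% surplus.

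**Precision of a split, at 20% dropout.** The half-width is 1.96 × √(0.2 × 0.8/n): 0.111 for n = 50 and 0.157 for n = 25. The exact 95% intervals are 10.0–33.7% (10/50) and 6.8–40.7% (5/25).

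**Bias against variance, 25 dialysis and 25 non-dialysis patients.**

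- 25% / 15%: overall SE = √(25 × 0.25 × 0.75 + 25 × 0.15 × 0.85)/50 = 5.6 points and bias 5, so RMSE = √(5² + 5.6²) ≈ 7.5. Dialysis-only SE = √(0.25 × 0.75/25) = 8.7.
- 30% / 10%: overall SE = √(25 × 0.3 × 0.7 + 25 × 0.1 × 0.9)/50 = 5.5 and bias 10, so RMSE ≈ 11.4. Dialysis-only SE = √(0.3 × 0.7/25) = 9.2.

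The overall figure is closer to the dialysis truth in the first case and further from it in the second.

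**The case against.** The strongest reply is that a single Background sentence carries the mismatch. The purpose, aims, design and population sections all speak of CKD, and neither Study Design nor General Methods says that the later trial is in ESRD/HD. Changing that sentence would remove the contradiction with no change to the analysis. This stands, and the fix allows for it.

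Second, at this sample size a split need not give a better estimate. The RMSE comparison confirms this for a modest gap, so a split should supplement the overall figures, not replace them. Three dialysis categories crossed with two drugs would average 50/6 ≈ 8 patients per cell.

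Third, dialysis status must be known in order to assign the bupropion regimen, so an analyst could produce the breakdown later. That is true, but none is planned and no minimum number protects its precision. The covariate score in General Methods does not fill the gap: it would include dialysis status only if that differed between arms and was related to outcome, and it yields no rate by dialysis status.

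A reader might also infer that the Research Plan restricts recruitment to dialysis centers. It does not: it names dialysis centers without excluding other sources, speaks of eligible CKD patients and gives a regimen for patients not on dialysis. The two source lists disagree, but that is an editorial inconsistency.

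**Conclusion.** The point holds as a cheap improvement. The Background aims at ESRD/HD, eligibility covers three groups with no HD minimum, and no planned output gives disposition, dropout or adverse events by dialysis status. The figures may therefore not describe the population for which the later trial is said to be designed.

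Two stronger readings go beyond the documents. A reader might infer that the estimates exclude the target population; in fact dialysis patients are enrolled, so they are diluted by an unknown amount, and tolerability is already reported by drug arm. A reader might also infer that the overall dropout rate will be too low and leave the later trial short. No passage says that dropout is higher on dialysis, and the adherence screens and on-site procedures could point the other way. The errors of 2.5 to 15 points, and the 12.5% shortfall or surplus, follow entirely from the assumed mix and rates.

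**What to change.** Keep the planned overall and by-arm tables. Add a descriptive breakdown of dialysis (HD and PD shown separately where numbers allow) versus non-dialysis for:

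- subject disposition;
- dropout, with a confidence interval;
- weeks of treatment completed;
- adverse-event rates.

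In the Background, either state that the dialysis rows inform an ESRD/HD trial, or restate the definitive trial's population as CKD. Make the source lists in the Recruitment Process and the Research Plan agree.

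The cost is wording and extra columns in tables already planned; no new data are needed. The drawback is imprecision in the smaller groups, so their figures should be labelled descriptive and read beside the overall ones.

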#### Choices of bupropion and fluoxetine for the treatment:

Bupropion is unique amongst antidepressants because it selectively blocks reuptake of NE and DA without having appreciable affinity for postsynaptic receptors including histamine, α- or β-adrenergic, 5-HT, or acetylcholine [30, 88]. This confers a favorable side effect and safety profile [89], absence of weight gain [90] or somnolence [91]; side effects frequently reported by HD patients with other antidepressants [92-95]. Bupropion has no clinically significant effects on the cardiovascular system (e.g., heart rate, blood pressure, QTc interval) in patients with MDD [96]. It can increase the incidence of seizures [97] in a dose-dependent (>450 mg/day) [30] fashion in patients with a history of seizures; therefore it is contraindicated in these patients. Bupropion may preferentially reduce a subset of symptoms of MDD common in medically ill patients, including fatigue, drowsiness, cognitive dysfunction, anhedonia, and mental concentration [98, 99]. In healthy humans, after oral administration, bupropion is rapidly and ~100% absorbed by the intestine, metabolized in the liver, and excreted via kidney. The hepatic cytochrome P450 (CYP) 2B6 catalyzes bupropion to a primary active metabolite, hydroxylbupropion. Several studies [62, 100, 101] have provided guidelines and recommendations about antidepressant agents in patients with ESRD/HD. One study [80] determined the PK of bupropion and its active metabolites in HD patients following a single 150-mg oral dose and found comparable PK profile to individuals with normal renal function. Compared with controls, hydroxyl-bupropion demonstrated a >2fold greater AUC and substantially increased t1/2, indicating reduced clearance. Based on these data, the authors [80] suggested an oral dose of 150 mg bupropion every 3 days in HD patients.

While it has been suggested that antidepressants may in general reduce inflammation, research data suggests that SSRIs and tricyclic antidepressants may not. Other hand, there has been considerable recent interest in the anti-inflammatory effects of bupropion, although more research is needed [102]. Brustolim et al. [33] demonstrated that bupropion significantly reduced the levels of TNF- $\alpha$  in mice challenged with lipopolysaccharide and suggested that this effect might have important clinical consequences. In case reports, Kast and Altschuler [35, 36] proposed the potential anti-inflammatory

Version #: 17, IRB #203076

PI: [name]

function of bupropion against TNF- $\alpha$  in patients with Crohn's disease and chronic hepatitis B virus infection. Bupropion has been found to be effective at both reducing inflammation and improving mood in patients with atopic dermatitis [34]. While Eller et al [103] found no effect of bupropion on TNF- $\alpha$  when it was added to ongoing escitalopram treatment, this study was in medically healthy MDD patients whose TNF- $\alpha$  levels were not much elevated, suggesting a possible "floor" effect. TNF- $\alpha$  is considered as a "master regulator" of the cytokine cascade in HD [48]. Given the well-established TNF- $\alpha$  elevation in HD, bupropion may be a uniquely well-suited antidepressant for these patients.

Fluoxetine is first SSRI approved by the Food and Drug Administration for treatment of MDD in the US. It is the most studied antidepressant in ESRD/HD patients [18, 20, 23, 27, 60-62] and has been found to be safe, tolerable, and to have some suggestive evidence of being efficacious. It may not reduce inflammation, [60, 104] and therefore will serve as a good comparator for bupropion.

